Aim 3: Compare the surgical time to complete one sinus side during functional endoscopic sinus surgery after the preoperative use of 0.05% Oxymetazoline or Epinephrine

Hypothesis: There will be no difference in surgical time

Study Design

The study will be a single center prospective randomized double blinded pilot study to compare blood loss and visualization of the surgical field following the preoperative use of pledgets soaked in Oxymetazoline or Epinephrine.

The inclusion criteria will be patients undergoing bilateral endoscopic sinus surgery (ESS) in which the same sinuses and procedures on both sides are the same for CRS with or without nasal polyposis. Exclusion criteria will be pregnancy, known coagulopathy, an international normalized ratio greater than 1.3, a partial thromboplastin time greater than 50 seconds, use of non-steroidal anti-inflammatory drugs in the last 10 days (2 or more doses), use of any antiplatelet agents (eg, warfarin, clopidogrel, berlinta) poorly controlled hypertension with a

preoperative systolic blood pressure of 160mm Hg or greater or a diastolic blood pressure of 90mm Hg or greater, or having any adverse reaction to topical epinephrine or oxymetazoline.

The study will be a paired design study with one nasal cavity receiving epinephrine and the other receiving oxymetazoline. The 1:1000 epinephrine and oxymetazoline solutions both comes in a 30cc vial and each pledget will be wrung out in a similar fashion to keep volume administered similar. The side each drug will be placed on will be randomized using a block randomization scheme on the day of surgery with a block size of four. Two pledgets with the associated medication will be placed into the nasal cavity; one along the floor of the nose and another directed towards the middle meatus.

As a part of routine preoperative workup all patients receive preoperative computed tomography scans of the paranasal sinuses with a navigation protocol. These scans will be assessed using the Lund-Mackay staging system, a standardized radiological grading system used to evaluate CT scans of chronic rhinosinusitis patients. The sinonasal mucosa will also be scored by the surgeon on the day of surgery using a mucosal grading system we have used previously which was modified from a mucosal grading system originally used for grading patients with allergic fungal rhinosinusitis.²

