No adverse events are anticipated. The study should provide no additional risk to the patient.

Any potential adverse events or unanticipated problems will be monitored by the research team and reported as discovered. The research team has a pre-scheduled monthly meetings where this study will be discussed.

Statistics

Statistical significance will be defined as less than 0.05. For quantitative data a 2-tailed paired t-test will be used. Categorical data will be compared using the McNemar's test. For non normally distributed data a Wilcoxon rank-sum test will be used. All patients who are administered both randomized preoperative topical vasoconstrictors will be included in the study.

The blood loss of 355 ± 393 mL seen in sevoflurane group from a previous study we performed in which we used oxymetazoline was used to calculate sample size.² With a proposed difference of 150ml of blood loss with a targeted power of 0.8 and a targeted Type 1 error rate of 5% a sample size of 50 was calculated we will plan to enroll 50 patients.

Ethics

No other IRB approval will be sought.

Informed consent will be obtained by one of the study investigators at the patient's preoperative visit in clinic or in the preoperative waiting area.

All data will be deidentified and assigned a random number. Data will be stored on a password protected file on a password protected computer.

Data handling and record keeping

All data will be deidentified and assigned a random number. Data will be stored on a password protected file on a password protected computer in the principal investigators office. All videos obtained will be de-identified and kept at the principal investigator's password protected computer in a locked office.

Quality control and assurance

Quality of video data and photographs will be assessed intraoperatively. A Storz representative will be available to aid with video equipment if technical difficulties were to occur.

There are no plans to have third party monitoring.

Publication Plan

We plan to submit the paper for publication to a high-quality ENT or Rhinology journal. Results will be available to the patients if requested.

References

1. Anderhuber, W., C. Walch, E. Nemeth, H. J. Semmelrock, A. Berghold, G. Ranftl, and H. Stammberger. "Plasma Adrenaline Concentrations during Functional Endoscopic Sinus Surgery." *The Laryngoscope* 109, no. 2 Pt 1 (February 1999): 204–7.

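### The blood-loss sample size applies what is most plausibly a whole-operation loss to a side-versus-side comparison without converting it, and the stated 0.8 power does not follow from the inputs

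*Combined protocol and SAP*

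**What the plan says.** The sample-size paragraph in the Statistics section of the combined protocol and SAP starts from one group of an earlier study by the same team: "The blood loss of 355 ± 393 mL seen in sevoflurane group from a previous study we performed in which we used oxymetazoline". The reference list shows that this study compared intravenous with inhalational anaesthesia. The paragraph continues: "With a proposed difference of 150ml of blood loss with a targeted power of 0.8". At a 5% significance level it arrives at 50 patients.

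The design is within-patient. The Study Design section says: "The study will be a paired design study with one nasal cavity receiving epinephrine and the other receiving oxymetazoline". It restricts entry to "patients undergoing bilateral endoscopic sinus surgery (ESS) in which the same sinuses and procedures on both sides are the same". The analysis matches the design: "For quantitative data a 2-tailed paired t-test will be used".

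The plan does not say whether 355 mL covers one side or both, or whether 150 mL is per side or per operation. It gives no per-side mean or SD, no SD of the within-patient difference and no correlation between sides. The description of blood-loss measurement, in which irrigation is subtracted from the suctioned volume, mentions no separate reading for each side.

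**The concern.** Type of anaesthesia is a property of the patient, not of a nostril. A mean loss reported for an anaesthetic group is therefore most naturally the loss for the whole operation. The quantity tested here is the difference between two sides of one operation. Moving from one to the other changes all three inputs: the expected loss per side is smaller, the SD of a side difference is not the SD of a total, and a given number of millilitres is a larger share of what a side loses.

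Without that conversion a reader cannot tell how large an effect 150 mL represents, or what power 50 patients have for it. Blood loss is the only endpoint with a sample-size basis in the plan, so this paragraph is the only statement of what the trial can detect.

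**Working it through.** **Inputs.** Mean 355 mL, SD 393 mL, difference 150 mL, power 0.8, type 1 error 5% and 50 patients come from Statistics. The two-sided paired t-test is also from Statistics, and the side-versus-side comparison in bilateral surgery is from Study Design. The correlation r between sides is not in the documents and is varied below.

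**Step 1: the plan's own figure.** Taking 393 mL directly as the SD of the paired difference, n = (SD × (1.960 + 0.842) / difference)² = (393 × 2.802 / 150)² = 53.9, so 54 patients, or 56 with the t distribution. One-sided versions give 43 and 44. Two independent groups would need 108 per arm. None of these gives 50. With 50 pairs, two-sided power is 0.754 (t) or 0.770 (normal). Power of 0.80 at n = 50 needs a side-difference SD of about 371 mL, which the plan does not state.

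**Step 2: the target as a share of expected loss.**
- Per-side figure: 150 / 355 = 42%.
- Bilateral total, split equally: 355 / 2 = 177.5 mL per side, and 150 / 177.5 = 84.5%.
- If half of the earlier operations were unilateral (an assumption), the mean per side is 355 / 1.5 = 237 mL, and 150 / 237 = 63%.

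**Step 3: the SD on the per-side scale, if 393 mL belongs to a bilateral total.** With equal side SD s, Var(total) = 2s²(1 + r) and Var(difference) = 2s²(1 − r). Hence SD of the difference = 393 × √((1 − r)/(1 + r)). The smallest difference detectable with 80% power in 50 pairs is 0.404 × that SD. The 75 mL column is 42% of 177.5 mL. It is shown for illustration only; the plan names no such effect.

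| Assumed r | SD of difference (mL) | Power, 150 mL | Power, 75 mL | Smallest detectable (mL; share of 177.5) |
|---|---|---|---|---|
| 0 | 393 | 75% | 26% | 159 (89%) |
| 0.25 | 304 | 93% | 40% | 123 (69%) |
| 0.5 | 227 | above 99% | 63% | 92 (52%) |
| 0.75 | 149 | above 99% | 94% | 60 (34%) |
| 0.8 | 131 | above 99% | 98% | 53 (30%) |

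**Step 4: if 355 ± 393 mL is already per side.** SD of the difference = 393 × √(2(1 − r)), which is 556, 481, 393 and 278 mL at r = 0, 0.25, 0.5 and 0.75. Power for 150 mL with 50 pairs is then 46%, 58%, 75% and 96%.

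**Reading the results.** An SD of the difference of 393 mL arises in two quite different situations: a bilateral total with r = 0, or a per-side figure with r = 0.5. The plan does not say which it assumes, if either. Across the two readings, power for 150 mL runs from 46% to above 99%.

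These figures assume a constant shift between sides and a paired t-test. With an SD larger than the mean for a loss that cannot be negative, the data are probably right-skewed, so the power figures are approximate.

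**The case against.** The documents never say that 355 mL is a bilateral total. They give the group's mean and SD and the title of the source study, nothing on how loss was recorded or how many sides were operated on. This stands: the whole-operation reading is a plausible inference, and 85% is conditional on it.

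A reader might infer that 150 mL is barely reachable, so that the trial can see only a near-abolition of bleeding. The documents do not support this. They give no expected effect against which to judge what is reachable. The inference also shrinks the mean to one side while leaving the SD at the whole-operation value. Once both are converted, 50 pairs may detect far less than 150 mL.

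A reader might also infer that the trial cannot see a proportionate reduction of about 75 mL per side. Power for that runs from 26% at r = 0 to 98% at r = 0.8. It reaches 80% when the side-difference SD is about 75 / 0.404 = 186 mL, which corresponds to r of about 0.64. Both sides share patient, anaesthetic and extent of surgery, so a low correlation cannot be presumed.

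Finally, 150 mL might be taken as a threshold of relevance. The plan calls it only a proposed difference and nowhere says that smaller differences do not matter.

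Blood loss is the secondary endpoint of a study that calls itself a pilot, which limits the weight of the point. What remains is that the scale is unstated and the claimed power cannot be recovered.

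**Conclusion.** The concern holds as a mismatch of scale and an unsupported power statement. The reference loss is most plausibly per operation, the comparison is per side, and none of the three inputs is converted. On an equal split of a bilateral total, 150 mL is 84.5% of a side's loss; on a per-side reading it is 42%.

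The stated 0.8 power is not what the plan's inputs give. It is about 75% if 393 mL is used as the SD of the difference (56 pairs would be needed for 80%), and 93% to above 99% if 393 mL is a bilateral total and r is 0.25 or more.

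The results rest on equal side variances, an equal split and an assumed correlation. They do not show that 50 patients are too few, or that a realistic effect would be missed. Severity is minor to moderate.

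**What to change.** Keep 50 patients and rewrite the sample-size paragraph:

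- State whether 355 ± 393 mL was recorded per operation or per side, and how many of those operations were bilateral. The team ran that study, so it is best placed to establish this.
- Put the reference mean, the SD and the target difference on the per-side scale. Give the target in millilitres and as a share of the expected loss on an oxymetazoline side.
- Replace the 0.8 power claim with the smallest per-side difference detectable with 80% power in 50 pairs: 0.404 × SD of the within-patient difference. State the assumed correlation. If 393 mL is the SD of a bilateral total, this is about 159, 92 and 53 mL at correlations of 0, 0.5 and 0.8. If it is already per side, the SDs of 556, 393 and 278 mL in Step 4 give 0.404 × SD of about 225, 159 and 112 mL at correlations of 0, 0.5 and 0.75.

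The cost is a change of wording, with no extra patients and no change to design or analysis. The downside is that the stated power becomes conditional on an assumed correlation and may look less favourable.
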